## **2.2 OBJECTIVES**

### **Primary**

1. To explore the efficacy of I+R combination as a therapeutic alternative to immuno-chemotherapy (R-CHOP regimen) in indolent forms of MCL by assessing the rate of complete responses achieved at 12 months of treatment.

### **Secondary**

[figure not shown]
1. To evaluate the efficacy of I+R combination along time in terms of secondary endpoints (ORR at 12 months, PFS, response duration, OS, MRD analysis)
2. To determine the safety and tolerability of ibrutinib in combination with rituximab (including evaluation of health-related quality of life (QOL))
3. Biological characterization of indolent forms of MCL and their response to I+R by genomic studies

### 3. STUDY DESIGN AND TREATMENT DESCRIPTION

#### 3.1 DEVELOPMENT PHASE

Phase II exploratory clinical trial.

#### 3.2 STUDY SCHEMA

Version 3.2: September 16th, 2020

### 3.3 TREATMENT PLAN

Subjects will receive ibrutinib in combination with rituximab according to the following schedule:

- Ibrutinib 560 mg daily po for 28 days (cycle one). Continuous cycles until disease progression or unacceptable toxicity. In case of sustained negative MRD (at least for 6 months) after 2 years of continuous therapy, ibrutinib will be discontinued.
- Rituximab 375 mg/m^2 iv day 1, 8, 15 and 22 (cycle 1, 4 doses). Rituximab 375 mg/m^2 iv, day one of every other cycle for 4 doses (cycle 3, 5, 7 and 9).

This clinical trial includes:

- Central review of response by imaging.
- Histological central laboratory review of diagnosis.
- Biological Associated Project.

Within a maximum of 28 days pre-treatment study test will be performed (except BMO and PET-CT, that are admissible if are obtained within six months and three months respectively in patients with clinical stability) and then the medication is started. Tests to be performed and related details are described in section 4.2 of this protocol.

#### **1. Patient Screening Procedure:**

Before starting the selection period, the patient's informed consent should be obtained, using the latest version in force throughout the entire trial. Different procedures performed as part of routine clinical management of the patient (e.g., blood tests, imaging tests, etc.) and made before the informed consent signature can be used for selection or basal if these tests were carried out as specified in this protocol. Once the informed consent is signed, a screening number will be assigned to each patient (screening code). Each site will receive in the Investigator Site File, the screening form in which default numbers are assigned for the screenings. This document must always remain in study site in the custody of the research team. This selection number will identify patients during the period from informed consent signature to the inclusion in the study.

#### **2. Patient Inclusion Procedure:**

After confirming that a patient is a candidate for inclusion in this study (inclusion / exclusion criteria), the inclusion (registration) procedure should be done centralized in MFAR.

The recruitment period will be of ~~3~~ **3.5** years (expected from ~~May~~**January** 2016 to ~~December~~**January** 2019).

**Version 3.2: September 16th, 2020**

The patient inclusion procedure is described below:

1. Complete and sign the inclusion form for the patient (the registration form must be signed by a clinical Principal Investigator or designated, appropriately identified in the signature list and registration delegation of responsibilities).

2. Send the completed and signed form to:

**MFAR, S.L.**

**FAX ([name]) o e-mail a [[contact]](mailto:[contact])**

3. MFAR, will carry out the registration process of the patient.

4. MFAR Will reply to sites, sending both by fax and email the inclusion confirmation

form for the patient. The inclusion confirmation form contains the patient code for this study, which will identify the patient throughout the trial.

5. Once the site staff has received form MFAR the inclusion confirmation form, the patient can start study treatment.

### 3.4 PROTOCOL MEDICATION

#### 3.4.1. Ibrutinib

Ibrutinib 560 mg daily po for 28 days (cycle one). Continuous cycles until disease progression or unacceptable toxicity. In case of sustained negative MRD (at least for 6 months) after 2 years of continuous therapy, ibrutinib will be discontinued.

Patients should take 4 capsules of ibrutinib (total dose 560 mg) once daily from D1, Cycle 1. The capsules should be administered orally with a glass of water, approximately at the same time each day. The capsules should be swallowed whole with water and should not open, break or chew. Patients should avoid the consumption of foods and beverages containing grapefruit and Seville oranges during the duration of the study due to the inhibition of cytochrome 3A4/5.

If the patient does not take a dose at the scheduled time, he/she can take it as soon as possible at same day and return to normal schedule the next day. The patient should not take extra capsules to make up for the missed dose.

Ibrutinib supply: Ibrutinib will be supplied by the Sponsor, through Janssen Laboratory.

#### 3.4.2. Rituximab

Rituximab 375 mg/m^2 iv day 1,8, 15 and 22 (cycle 1, 4 doses). Rituximab 375 mg/m^2 iv, day one of every other cycle for 4 doses (cycle 3, 5, 7 and 9).

Before Rituximab infusion, it is recommended to administer Site local practise pre-medication that includes: se recomienda administrar pre-medicación habitual de cada centro que incluya:

1. Antipyretic
2. Antihistaminic
3. Optionally, up to the investigator's discretion the use of glucocorticoids (i.e.: methylprednisolone 60 mg iv) as part of the pre-treatment and in case of rituximab reaction.

Rituximab administration will be done by intravenous infusion. The prepared solution should be administered as an intravenous infusion through a dedicated line. It should not be administered as an intravenous push or bolus. The first infusion will begin at a rate of 50 mg/hour after the first 30 minutes, it could be done increments of 50 mg / hr every 30 minutes to a maximum of 400 mg/hour. Subsequent infusions can be infused at an initial rate of 100 mg / hr being increased to 100 mg / hour at intervals of 30 minutes to a maximum of 400 mg / hour.

Rituximab supply: Rituximab, treatment commercially available and indicated in all MCL national and European guidelines will be provided by participating Hospital through the local supply procedure, after positive vote of the EC and Institution Conformity.

### 3.4.3 Ibrutinib possible adverse events

The following information detailed the possible adverse events of Ibrutinib. It should also consider the information regarding contraindications, warnings, precautions for use and possible interactions with other drugs, available at:

- Last version of Investigator Brochure available at Investigator Site File.
- Last Version of Summary of Product Characteristics (SmPC), available at the Investigator Site File or at EMA website:

<http://www.ema.europa.eu>

### 3.4.4 Possible adverse events of other drugs used in the trial

For the rest of drugs administered to trial subjects, it should be considered the information regarding contraindications, warnings, precautions for use and possible interactions, available at:

- Summary of Product Characteristics (SmPC), available at the Investigator Site File or at EMA website:

<http://www.ema.europa.eu>

## 3.5 DOSE ADJUSTMENTS

### 3.5.1. Ibrutinib Dose adjustments

Ibrutinib therapy should be withheld for any new onset or worsening grade  $\geq 3$  non-haematological toxicity, grade 3 or greater neutropenia with infection or fever, or grade 4 haematological toxicities. Once the symptoms of the toxicity have resolved to grade 1 or baseline (recovery), Ibrutinib therapy may be reinitiated at the starting dose. If the toxicity reoccurs, the once daily dose should be reduced by one capsule (140 mg). A second reduction of dose by 140 mg may be considered as needed. If these toxicities persist or recur following two dose reductions, discontinue the medicinal product.

Recommended dose modifications are described below:

Dose level	Dose
0	560 mg/day
-1	420 mg/day
-2	280 mg/day
Discontinue Ibrutinib	

### Missed dose

If a dose is not taken at the scheduled time, it can be taken as soon as possible on the same day with a return to the normal schedule the following day. The patient should not take extra capsules to make up the missed dose.

### 3.5.2 Rituximab dose adjustment

The increase or reduction in dose infusions is not contemplated. Mild or moderate infusion-related reactions usually resolve by reducing the infusion rate and increasing it when symptoms improve.

Patients should be closely monitored for detecting the start of a cytokine release syndrome. The infusion should immediately stop in patients who develop any evidence of severe reactions, especially severe dyspnoea, bronchospasm or hypoxia. Then it should be evaluated the evidence of tumor lysis syndrome including appropriate laboratory tests, and evidence of pulmonary infiltration by chest radiography. No patient infusion should be restarted until complete resolution of all symptoms, and normalization of laboratory values and chest x-ray results. From that moment, the infusion may initially restarted at most half the rate of previous infusion. If the same severe adverse reactions would be presented for a second time, the decision to stop treatment, it should be discussed with the trial chief Investigator ([contact]), on a case by case basis.

It has been reported that, following IV administration of murine proteins, anaphylactic and hypersensitivity reactions can be observed, which typically occur during the first minutes of the infusion. It is convenient to have for immediate use, drugs used to combat hypersensitivity reactions, i.e., epinephrine, antihistamines and corticosteroids, in case an allergic reaction occurs during administration. Clinical manifestations of anaphylaxis may appear similar to clinical manifestations of cytokine release syndrome (described above). Reactions attributed to hypersensitivity have been reported less frequently than those attributed to cytokine release.

Since hypotension may occur during rituximab infusion, it should be considered to withhold anti-hypertensive medicines 12 hours prior to the infusion. It has been described angina pectoris or cardiac arrhythmias such as flutter and atrial fibrillation, heart failure or myocardial infarction in patients treated with rituximab. Therefore, patients with a history of cardiac disease and/or cardiotoxic chemotherapy, should be closely monitored.

Reactivation of hepatitis B, which included cases of fulminant hepatitis in patients who were treated with rituximab with cytotoxic chemotherapy have been observed. When rituximab is used in combination with cytotoxic chemotherapy, patients with a history of hepatitis B should be closely monitored for signs of active infection by the hepatitis B virus, and start antiviral treatment if clinically indicated.

### 3.6 TREATMENT WITHDRAWAL CRITERIA

In the event of sustained negative MRD (at least 6 months) after 2 years of continuous treatment, the investigator should withdraw ibrutinib treatment.

In addition, the investigator, for reasons of medical urgency, must withdraw the patient from the study treatment according to the following criteria:

1. Disease Progression: Patients that present progression will discontinue the treatment
2. Unacceptable toxicity
- ~~3. Negative MRD at least for 6 months after 2 years of treatment~~

**3.4. Patient non-compliance** ~~Investigator decision~~

**4.5.** Patient rejection to continue study treatment

Patients who complete treatment will undergo the end-of-treatment testing and evaluation schedule as described in section 5.2.4

Version 3.2: September 16th, 2020

### 3.7 CONCOMITANT TREATMENTS

Concomitant treatments include all prescription and non-prescription drugs used by the patient from 7 days before starting the study treatment until 30 days after the last study medication. The attending physician will prescribe the necessary treatments appropriate to concomitant diseases presented by any patient included in the study. The patient must inform to the investigator and record all concomitant medications in the relevant eCRF.

Patients using oral contraceptives, hormone replacement therapy or other maintenance treatments, should continue using it.

#### a. Treatment and prophylaxis for neutropenia

In this study the use of G -CSF to treat neutropenia is allowed.

Primary prophylaxis with G -CSF is recommended under the guidelines of ASCO, EORTC, ESMO and(15).

#### b. Hepatitis B reactivation prophylaxis

Lamivudine or other antiviral treatments have to be considered to patients at risk of reactivation of hepatitis B (i.e. HBcAc+).

#### c. Antimicrobial prophylaxis

It is recommended the use of antimicrobial prophylaxis (ie pneumonia prophylaxis by pneumocystis with sulfamethoxazole and trimethoprim or equivalent), according to Sites local guidelines

#### 3.7.1 Ibrutinib Interaction with other medicinal products and other forms of interaction

You can obtain detailed information in:

- Last version of Investigator Brochure available at ISF
- Last version of Summary of Product Characteristic available at ISF and at EMA website:

[https://www.ema.europa.eu/en/documents/product-information/imbruvica-epar-product-information\\_es.pdf](https://www.ema.europa.eu/en/documents/product-information/imbruvica-epar-product-information_es.pdf)

#### 3.7.2 Rituximab Interaction with other medicinal products and other forms of interaction

It should take into account information on possible interactions with other drugs for other therapeutic drugs referred to in the trial scheme, available at:

Summary of product characteristics available at the investigator site file or at EMA website:

<http://www.ema.europa.eu>

## 4. PATIENT ELIGIBILITY CRITERIA

### 4.1 INCLUSION CRITERIA

1. Subjects with confirmed diagnosis of Mantle Cell Lymphoma (World Health Organization Classification, WHO 2008). Classical, small-cell variants and marginal-zone variants can be included.
2. Age 18 years or older.
3. Subjects must not have received any prior therapies (excluding diagnostic splenectomy).
4. Asymptomatic patients.
5. Ann Arbor clinical stages I-IV.
6. Eastern Cooperative Oncology Group (ECOG) performance status <2 (0-1).
7. Subjects with a non-nodal MCL presentation with mainly bone marrow or peripheral blood involvement.
8. Other asymptomatic clinical presentations are acceptable in case of low tumor burden, including nodal MCL with lymph node enlargement  $\leq 3$  cm in the maximum diameter and with low proliferation index (Ki-67  $\leq 30\%$ ).
9. The following laboratory values at screening:
  - Neutrophil count  $\geq 1 \times 10^9/L$ , Hemoglobin level  $\geq 100$  g/L or platelet count  $\geq 100 \times 10^9/L$
  - Transaminases (AST and ALT)  $\leq 3 \times$  ULN
  - Total bilirubin  $\leq 1.5 \times$  ULN unless bilirubin rise is due to Gilbert's syndrome or of non-hepatic origin
  - Creatinine  $\leq 2 \times$  ULN or calculated creatinine clearance  $\geq 40$  mL/min/1.73m^2
10. Stable disease without evidence of clinical progression criteria for at least 3 months. Patients in prolonged therapeutic abstention may be included.
11. Women of childbearing potential and men who are sexually active must be practicing a highly effective method of birth control during and after the study consistent with local regulations regarding the use of birth control methods for subjects participating in clinical trials. Men must agree to not donate sperm during and after the study. For females, these restrictions apply for 1 month after the last dose of study drug. For males, these restrictions apply for 3 months after the last dose of study drug.
12. Women of childbearing potential must have a negative serum (beta-human chorionic gonadotropin [ $\beta$ -hCG]) or urine pregnancy test at Screening. Women who are pregnant or breastfeeding are ineligible for this study.
13. Sign (or their legally-acceptable representatives must sign) an informed consent document indicating that they understand the purpose of and procedures required for the study, including biomarkers, and are willing to participate in the study.

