## 5. STUDY DEVELOPMENT AND RESPONSE ASSESSMENT

### 5.1 STUDY ENDPOINTS

#### Primary Endpoint:

1. Rate of complete remission (CR) achieved at 12 months with Ibrutinib in combination with Rituximab. All the patients will be evaluated with PET-CT and bone marrow biopsy at that point and the international response criteria will be applied (13).

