**ANNEX VII. Revised Criteria for Response Assessment**

Lugano Criteria for Response Assessment for Non-Hodgkin Lymphoma (13)

Response and Site	PET-CT–Based Response	CT–Based Response
Complete	Complete metabolic response	Complete radiologic response
Lymph nodes and extralymphatic sites	Score 1, 2, or 3 with or without a residual mass on 5PS†  It is recognized that in Waldeyer's ring or extranodal sites with high physiologic uptake or with activation within spleen or marrow (eg, with chemotherapy or myeloid colony-stimulating factors), uptake may be greater than normal mediastinum and/or liver. In this circumstance, complete metabolic response may be inferred if uptake at sites of initial involvement is no greater than surrounding normal tissue even if the tissue has high physiologic uptake	Target ganglia / ganglion masses should decrease by $\leq 1.5$ cm in LDi No extralymphatic sites of disease
Non Measured lesion	Not applicable	Absent
Organ enlargement	Not applicable	Back to normal
New lesions	None	None
Bone marrow	No evidence of FDG-avid disease in marrow	Normal by morphology; if indeterminate, IHC negative
Partial	Partial metabolic response	Partial radiologic response
Lymph nodes and extralymphatic sites	Score 4 or 5† with reduced uptake compared with baseline and residual mass(es) of any size At interim, these findings suggest responding disease At end of treatment, these findings	$\geq 50\%$ decrease in SPD of up to 6 measurable target nodes and extranodal sites. When a lesion is too small to measure on CT, assign 5mm $\times$ 5mm as the default value.

	indicate residual disease	When no longer visible, 0 × 0 mm. For a node > 5mm × 5mm, but smaller than normal, use the actual measurement for the calculation.
Non Measured lesions	Not applicable	Absent / normal, regress, but no increase
Organ enlargement	Not applicable	None
New lesions	None	Not applicable
Bone marrow	Residual uptake higher than uptake in normal marrow but reduced compared with baseline (diffuse uptake compatible with reactive changes from chemotherapy allowed). If there are persistent focal changes in the marrow in the context of a nodal response, consideration should be given to further evaluation with MRI or biopsy or an interval scan	Not applicable
No response or stable disease	No metabolic response	Stable disease

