Target nodes/nodal masses, extranodal lesions	Score 4 or 5 with no significant change in FDG uptake from baseline at interim or end of treatment	<50% decrease from baseline in SPD of up to 6 dominant measurable nodes and extranodal sites; criteria for disease progression are not met
Non Measured lesions	Not applicable	No increase consistent with progression
Organ enlargement	Not applicable	No increase consistent with progression
New lesions	None	None
Bone marrow	No change from baseline	Not applicable
Progressive disease	Progressive metabolic disease	Progressive disease requires at least 1 of the following
Individual target	Score 4 or 5 with an increase in	A single node / lesion must be

nodes/nodal masses	intensity of uptake from baseline and/or	abnormal with: LDi > 1.5 cm and ≥50% increase from PPD nadir and An increase in LDi or SDi from nadir 0.5 cm for lesions ≤ 2 cm 1.0 cm for lesions > 2 cm In the setting of splenomegaly, splenic length should increase by > 50% of the extent of its previous increase beyond the baseline (eg, a 15 cm spleen should increase to > 16 cm). If there is no previous splenomegaly, it should increase at least 2 cm from the initial value New or recurrent splenomegaly
Extranodal lesions	New FDG-avid foci consistent with lymphoma at interim or end-of-treatment assessment	
Non Measured lesions	None	New progression or clear progression of unmeasured pre-existing lesions
New lesions	New FDG-avid foci consistent with lymphoma rather than another etiology (eg, infection, inflammation). If uncertain regarding etiology of new lesions, biopsy or interval scan may be considered	Regrowth of previously resolved injuries. A new node > 1.5 cm on any axis. A new extranodal site > 1.0 cm in any axis; if it is < 1.0 cm in any axis, its presence must be unequivocal and attributable to lymphoma Assessable disease of any size unequivocally attributable to lymphoma
Bone marrow	New or recurrent FDG-avid foci	New or recurrent alteration

Abbreviations: 5PS, 5-point scale; CT, computed tomography; FDG, fluorodeoxyglucose; IHC, immunohistochemistry; LDi, longest transverse diameter of a lesion; MRI, magnetic resonance imaging; PET, positron emission tomography; PPD, cross product of LDi and perpendicular diameter; SDi, shortest axis perpendicular to LDi; SPD, sum of the product of the perpendicular diameters for multiple lesions.

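### Patients entering as low-burden disease need no evaluable disease at baseline, so a marrow-negative patient already meeting the PET-CT and marrow definition of CR at screening can count as a 12-month success

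*Protocol*

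**What the plan says.** **Entry (Protocol 4.1 and 4.2).** Inclusion 1 asks for "Subjects with confirmed diagnosis of Mantle Cell Lymphoma (World Health Organization Classification, WHO 2008"), which concerns diagnosis and not remaining disease. Two routes follow. Inclusion 7 is the non-nodal route: "Subjects with a non-nodal MCL presentation with mainly bone marrow or peripheral blood involvement". Inclusion 8 is the other: "Other asymptomatic clinical presentations are acceptable in case of low tumor burden, including nodal MCL with lymph node enlargement" of at most 3 cm, with Ki-67 at most 30%. Inclusion 5 accepts "Ann Arbor clinical stages I-IV". Inclusion 3 reads "Subjects must not have received any prior therapies (excluding diagnostic splenectomy"). The exclusions remove larger nodes, symptoms, cytopenias due to the lymphoma and monoclonal lymphocytosis with the MCL phenotype. None asks for a minimum node size, an FDG-avid site or a positive marrow.

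**Endpoint (5.1, 5.3.2, 5.5).** The primary endpoint is the percentage of patients alive and in CR 12 months after starting treatment. "All the patients will be evaluated with PET-CT and bone marrow biopsy at that point", and section 5.5 uses the 12-month biopsy to confirm CR. PET-CT and biopsy are also done at screening, but no entry rule and no part of the CR definition uses their result.

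**CR definition (Annex VII).** The PET-CT column grants CR to nodes and extralymphatic sites with "Score 1, 2, or 3 with or without a residual mass on 5PS". The CT column needs target nodes of at most 1.5 cm, non-measured lesions absent and a normal marrow.

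**Decision rule (section 7).** The reference CR rate is 30% with R-CHOP. Fifteen patients enter stage 1, and the trial stops at 5 or fewer CRs. The total is 50, with at least 46 evaluable for response. Section 7 does not define evaluable, and it states no final cut-off.

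**The concern.** In a single-arm trial the CR rate is read as drug effect because CR should mean that disease was present and has gone. That reading fails for a patient with nothing at baseline that PET-CT or biopsy could show clearing. If such a patient stays stable, which inclusion 10 selects for by asking for at least 3 months without progression, the 12-month assessment returns CR whatever the drugs do. Nothing in the protocol indicates that the 30% reference rate included such patients, so each one tilts the comparison in favour of the combination.

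**Working it through.** **1. Who can meet the definition at screening.**
- Marrow involved (most of the inclusion 7 route): not in CR at baseline, and the 12-month biopsy must clear. Not affected.
- Inclusion 8, marrow negative, only site excised for diagnosis, or involved spleen removed: no residual lesion, so CR by either column of Annex VII.
- Inclusion 8, marrow negative, small nodes scoring 1 to 3: CR by the PET-CT column. Not automatically CR by the CT column, because Annex VII lists nodes too small to measure but still abnormal as unmeasured lesions, and these must be absent.

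The exposed group is therefore marrow-negative patients, mainly through inclusion 8.

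**2. Reproducing the design.** Inputs from section 7: p0 = 0.30, p1 = 0.30 + 0.20 = 0.50, alpha 0.10, beta 0.20, n1 = 15 (stop at 5 or fewer), 46 evaluable. An exact search for the Simon optimal design gives:
- one-sided alpha 0.05: 5/15 then 18/46, exact alpha 0.0499, power 0.803. This matches 15 and 46.
- one-sided alpha 0.10: 5/15 then 12/32, exact alpha 0.0997, power 0.804. This does not match 46.

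The final rule used below, success at 19 or more of 46, is the one the stated sizes imply. It remains an assumption.

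**3. Effect of a share q already in CR at baseline and still in CR at assessment.** With a true CR rate of 0.30 in the others, the observed rate is

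p = q + (1 − q) × 0.30 = 0.30 + 0.70q.

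P(pass stage 1) = P(X ≥ 6), X ~ Bin(15, p).

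P(success) = Σ over x = 6 to 15 of P(X = x) × P(Y ≥ 19 − x), Y ~ Bin(31, p), since 46 − 15 = 31.

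| q | Patients of 46 (46q) | p | Pass stage 1 | False success |
|---|---|---|---|---|
| 0 | 0 | 0.300 | 0.278 | 0.050 |
| 5% | 2.3 | 0.335 | 0.387 | 0.125 |
| 10% | 4.6 | 0.370 | 0.501 | 0.248 |
| 15% | 6.9 | 0.405 | 0.612 | 0.407 |

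At q = 5% the chance of false success is already above the alpha of 0.10 stated in section 7. The observed rate would reach the 50% target with no added drug effect at q = (0.50 − 0.30)/0.70 = 28.6%.

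**4. Limits of the model.** It applies one rate to both stages, although stage 1 is read at 6 months by CT and marrow aspirate, and the endpoint at 12 months by PET-CT and biopsy. The stage-1 column therefore fits excised or splenectomised patients better than patients with small non-avid nodes. It also gives every exposed patient a CR with certainty, so deaths, missed assessments and progressions would lower the figures.

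**The case against.** **Lower limits exist.** Inclusion 7 names marrow or blood involvement, exclusion 3 removes monoclonal lymphocytosis, inclusion 8 speaks of enlarged nodes, and inclusion 10 of stable disease. This stands in part: it would be wrong to infer that the criteria set upper limits only. But inclusion 7 does not bind patients entering by inclusion 8, and exclusion 3 sets no amount of evaluable disease. Inclusion 8 accepts low-burden presentations generally, with nodal disease as one example, and gives no size floor.

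**Annex VII does not call every small node normal.** A reader might infer from "LDi > 1.5 cm and ≥50% increase from PPD nadir" that nodes up to 1.5 cm are never abnormal. That line belongs to the progression criteria, and the notes on unmeasured lesions say otherwise. This stands, and it confines the small-node case to the PET-CT column.

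**The share is unknown.** This stands. The protocol gives no basis for 5 to 15%, and many patients will probably have marrow or blood disease. The table shows sensitivity to q, not a measured bias.

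**The evaluable set may be defined in the SAP.** The protocol does foresee patients not evaluable for response. But it fixes eligibility and the CR definition itself, and the two together admit these successes. The figure of 46 is not tied to baseline disease and so does not close the gap.

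**It is late to change entry.** The synopsis calendar puts the end of recruitment at December 2019, and this version is dated September 2020. This stands, and it moves the remedy from eligibility to the analysis set.

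**Conclusion.** The point holds for one group: marrow-negative patients, mainly entering through inclusion 8, including those with an excised site or a removed spleen, who already satisfy the PET-CT and marrow definition of CR at screening. Sections 4.1 and 4.2 admit them, and section 5.3.2 counts them as successes against the 30% reference. The documents do not show that such patients were enrolled, or how many.

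The size is conditional. With a true 30% CR rate in the others, the implied but unstated 18/46 cut-off, and certain CR in the exposed patients, the chance of false success rises from 0.05 to 0.125, 0.25 and 0.41 at q = 5, 10 and 15%. Two or three patients among 46 are enough for the first step.

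A reader might infer that anyone meeting the imaging definition at entry is a free CR. The documents do not support that, because marrow-positive patients must clear the biopsy.

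**What to change.** In 5.3.2 and section 7, define the CR-evaluable set (the 46 or more evaluable patients) as patients with at least one disease site documented at baseline by a method repeated at the response assessment: an abnormal node or lesion on CT, an FDG-avid lesion, or marrow involvement on biopsy or aspirate. Exclude patients without such a site from numerator and denominator, apply the same rule to the 15-patient stage-1 count, and report the all-treated CR rate as a sensitivity analysis. If any enrolment remains, add the requirement to 4.1 and the synopsis.

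Keeping these patients in the denominator as non-responders is not a good alternative. It swaps in the opposite bias: with a true 50% CR rate in the others, the observed rate is 0.50 × (1 − q), and power under the same rule falls from 0.80 to 0.72, 0.62 and 0.50 at q = 5, 10 and 15%.

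The cost is low. Baseline PET-CT and biopsy are already required, and set membership depends only on screening findings, so it can be settled without reference to response. The downside is a slightly smaller evaluable set and possibly a slightly lower CR rate. The margin is 50 − 46 = 4 patients, or 8% of those enrolled, for all reasons of non-evaluability together.
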